15.0 CLINICAL AND LABORATORY EVALUATIONS AND PROCEDURES

15.1 Medical History

Medical history will include significant medical conditions and surgical history, medications taken within 2 weeks prior to signing the Informed Consent, and signs and symptoms occurring within 3 weeks after signing the Informed Consent.

15.2 Physical Examination and Vital Signs

A complete physical examination will be performed (including a genital/rectal exam if clinically indicated).

Vital signs will include oral temperature, blood pressure at rest, heart rate, and respiratory rate (and Weight for Weeks -3, and Mos. 12, 24).

15.3 Safety Laboratory

All safety laboratory evaluations will be conducted at the laboratories located at or associated with the clinical site. At every sampling time point, approximately 5 mL of blood will be drawn for each of the hematology and serum chemistry panels.

The following laboratory evaluations will be performed:

- Hematology Panel: hematocrit, hemoglobin, WBC, platelet count, lymphocyte count, neutrophil count
- Serum Chemistry Panel: sodium, chloride, calcium, potassium, magnesium, bicarbonate, lactate, C-reactive protein, glucose, creatinine, BUN, AST, ALT, alkaline phosphatase, and total bilirubin
- Lipid Panel: total cholesterol, LDL cholesterol, HDL cholesterol, and triglycerides
- Cytokines: Plasma TNF-α, Plasma IL-6, and Plasma IFN-γ
- INR

15.4 Pregnancy Test: Serum or urine β-hCG

- Serum β -hCG at Screening 1 (using same blood draw as for serum chemistry)
- Urine β-hCG at Baseline

15.5 Antibodies to HLA Antigens on SB623

• A serum sample, taken at initial screening (and optionally at a Pre-Screening visit) will be used to determine the presence of antibodies to donor SB623 cells with a Luminex value of >1000 MFI (Maximum Fluorescence Intensity): HLA Class I (HLA-A*23:PWMV, HLA-A*68:CGBR; HLA-B*45:FJH, HLA-B*53:KJW; or HLA-Bw4, HLA-Bw6; HLA-Cw*04:SSWB, HLA-Cw*16:01); or Class II (HLA-DRB1 *13:NGUB, HLA-DRB1 *16:02; HLA-DQB1*05:CHZY, HLA-DQB1*05:BK; HLA-DQA1*01:DVB, HLA-DQA1*X, HLA-DRB3,4,5: 3*03:01, HLA-DRB3,4,5: 5*02:02)

15.6 Serum Antibodies to SB623

Serum antibody measurements will be made to monitor a possible humoral-mediated immune response. Blood samples (approximately 10 mL) will also be taken at the intervals indicated in Table 4 for measurements of serum antibodies to SB623 using the Luminex assay. Assays may be done bimonthly on pooled samples.

15.7 PBMC Function

PBMC function will be evaluated to monitor any possible cell-mediated immune responses, including inflammation.

Blood samples (approximately 20 mL) will also be taken at the intervals indicated in Table 4. PBMCs from Baseline Samples will be aliquoted into approximately 20 tubes to provide at least 600,000 cells per tube, then kept frozen in vapor phase of liquid nitrogen until needed as controls for subsequent time-point assays. For all other time points, PBMCs will be isolated and the sample split into multiple vials of equal portions (A and B) containing at least 600,000 cells each, then similarly frozen until time to assay PBMC function. PBMC function during the study will be determined on the A portions by stimulation with PMA/ionomycin/SB623, evaluating any changes from baseline in cytokine secretion. These evaluations on batched samples of PBMCs will be approximately at bimonthly intervals during the first 6 months, quarterly thereafter through the first year, then at 2 years.

B portions of PBMCs will be stored in the vapor phase of liquid nitrogen until requested by the Sponsor for any subsequent determination of PBMC function if needed for further safety follow up.

15.8 Clinical Stroke Evaluations

15.8.1 European Stroke Scale (ESS)

Specific information on scoring using the ESS³¹ can be found in the publicatin.

15.8.2 National Institute of Health (NIH) Stroke Scale

Specific information on scoring using the NIH Stroke Scale⁵⁶ can be found in the publication.

15.8.3 Modified Rankin Scale (MRS)

Specific information on scoring using the MRS^{34,35} can be found in the publications.

15.8.4 Fugl-Meyer Score

Specific information on scoring using the Fugl-Meyer Scale³⁸ can be found in the publication.

15.9 Cognitive Questionnaire

A battery of tests will be used to evaluate cognitive function. These are summarized in Table 7, Appendix D, Section 23.0. Additional details will be provided by the Sponsor.

15.10 Assessment of Cellular Metabolism

Functional assessment of cells within and around the infarct will be determined by use of ¹⁸F-fluorodeoxyglucose uptake measured by positron emission tomography (PET).

16.0 ADVERSE EVENTS

16.1 General Information

An **adverse event** (AE) is any untoward medical occurrence in a patient or clinical investigation subject administered a pharmaceutical product and that does not necessarily have a causal relationship with this treatment. An AE can therefore be any unfavorable and unintended sign, symptom, or disease temporally associated with the use of an investigational product, whether or not considered related to the investigational product. This includes any side effects, injury, toxicity, or sensitivity reaction, and may include a single symptom or sign, a set of related symptoms or signs, or a disease. An adverse event is also any laboratory abnormality judged to be clinically significant by the Investigator or Sub-investigator(s) that worsened compared to Baseline.

Throughout the course of the study, every effort should be made to remain alert to possible adverse experiences. Patients should be encouraged to report adverse events spontaneously or in response to general, non-directed questioning.

With the occurrence of an adverse event, the primary concern is the safety of the patient. If necessary, appropriate medical intervention should be provided, and the investigational drug discontinued.

An AE **does not** include:

- Medical or surgical procedures (*e.g.*, surgery, endoscopy, tooth extraction, transfusion); the condition that leads to the procedure is an adverse event
- Pre-existing diseases or conditions present or detected at the start of the study that do not worsen in severity or frequency
- Situations where an untoward medical occurrence has not occurred (*e.g.*, hospitalization for elective surgery, social and/or convenience admissions)
- Overdose of either Study Drug or concomitant medication without any signs or symptoms

A Serious Adverse Event (SAE) is any adverse event that results in any of the following:

- death,
- life-threatening event,
- hospitalization or prolongation of hospitalization,
- a persistent or significant disability/incapacity,
- congenital anomaly/birth defect, or
- an event that may require intervention to prevent any one of the other outcomes listed above (based on medical judgment)

An **Unexpected Adverse Event** is any AE that is not identified in nature, severity, or frequency in the current Investigator's Drug Brochure or product information. For this study, an unexpected adverse event also includes neurological deterioration, procedural complications, seizures, benign and malignant tumors and pregnancy, and will be submitted as expedited reports.

An Unexpected Adverse Drug Reaction (ADR) is an adverse reaction, the nature or severity of which is not consistent with the applicable product information (*e.g.*, Investigator's Brochure for an unapproved investigational medicinal product). All noxious and unintended responses to a medicinal product related to any dose should be considered ADRs. All serious and unexpected ADRs will have expedited reporting to the FDA.

16.2 Adverse Event Reporting Period

The adverse event reporting period for this trial begins upon receiving the first dose of Study Drug and ends 24 weeks after the administration of SB623.

All AEs (both serious and non-serious) must be followed until resolution or until a stable clinical endpoint is reached. All measures required for AE management and the ultimate outcome of the AE must be recorded in the source document and reported to the Sponsor.

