7.0 SURGICAL AND IMPLANTATION PROCEDURES

The surgical procedure is a modification of one used earlier with another cell product,^{29,54} and which has been shown to have a high degree of safety in a retrospective study of over 2,600 patients undergoing stereotactic surgery over the course of 28 years at one major clinic.³⁰ On the morning of surgery, a standard stereotactic coordinate frame (Leksell Stereotactic System®, manufactured by Elekta⁵⁵) is to be applied to the head under local anesthesia and mild sedation. Either a head CT scan overlaid on the Baseline MRI or a head MRI scan alone is to be performed for stereotactic targeting. The MRI scans are to use insulated posts an RIF transmitter head, and 1.5 tesla. A safe trajectory is to be defined to enter a cortical gyrus, sparing a sulcus. Points are to be determined in the basal ganglia inferior to the stroke and beyond the stroke. Three needle tracks are to be determined with trajectories in the same paramedian plane spaced by 5-6 mm at the target

One burr-hole craniostomy (1-1.5 cm) is to be fashioned under local anesthesia. The dura is to be opened and a 1.8-mm outer-diameter. 15-cm long stabilizing cannula containing a removable solid stylet is to be inserted to a point just proximal to the penumbra of the stroke area. The solid stylet is then to be removed, followed by insertion into the stabilizing cannula of a 0.9-mm outer diameter, 19-cm. long, 20-µL volume Pittsburgh Implantation Cannula (previously qualified for product stability and delivery and provided by the Sponsor) down to the deepest target point for the first implantation. A total volume of 100 μ L of cell suspension is to be aspirated into a 100- μ L syringe through the implant cannula. The implantation cannula is then to be filled with cell suspension. Five 20-µL volumes of cells are to be injected slowly (approximately 10 μ L/min.) into 5 implantation sites, slowly withdrawing the stabilizing needle probe so that the implantations are spaced as equally as possible (intervals of 4-5 mm) with 2-3 implants within the penumbra distal to the stroke area and 2-3 implants within the penumbra proximal to the stroke area. The target locations will be selected by the site neurosurgeon and neurologist to be closest to the motor pathway based on the patient's own neuroanatomy. This procedure is to be repeated with 2 other needle tracks with different trajectories, inserted through the same burr-hole craniostomy.

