8.0 PATIENT SELECTION

8.1 Inclusion Criteria

- 1. Age 18-75 years
- 2. Documented history of completed ischemic stroke in subcortical region of MCA or lenticulostriate artery with or without cortical involvement, with correlated findings preferably by MRI or by CT if MRI is contraindicated
- 3. Between 6 and 60 months post-stroke, and having a motor neurological deficit
- 4. No significant further improvement with physical therapy/rehabilitation (confirmed by no change in NIHSS greater than ±1 within three weeks prior to enrollment)
- 5. Modified Rankin Score of 3 or 4
- 6. NIH Stroke Scale score of >7
- 7. Two evaluations during prior 3 weeks with no more than ±1 point change in clinical evaluation using the NIH Stroke Scale
- 8. Able and willing to undergo computed tomography (CT), magnetic resonance imaging (MRI), and positron-emission tomography (PET) scans of the head
- 9. Agree that use of antiplatelet, anti-coagulant, or non-steroidal anti-inflammatory drugs to be determined by the local medical staff and in accordance with the ACCP 2012 guideline "Perioperative Management of Antithrombotic Therapy: Antithrombotic Therapy and Prevention of Thrombosis, 9th Edition: American College of Chest Physicians Evidence-Based Clinical Practice Guidelines", if applicable¹, provided that no antiplatelet, anti-coagulant, or non-steroidal anti-inflammatory drugs are to be restarted after surgery until after the Day 8 MRI is read and determined to be safe to re-start
- 10. Normal emotional status; *i.e.*, no disabling psychological deficits
- 11. Ability of patient or legal authorized representative to understand and sign an Informed Consent

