18.0 STATISTICAL METHODS

18.1 Overview of Analysis

18.1.1 Safety Parameters

- Adverse events related to the surgical procedure
- SB623-related adverse events
- Adverse changes imaged by head MRI (edema, adverse anatomical changes)
- Serious adverse events (SAEs)
- Serum chemistry and hematology

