7.2.6 Medical History

Medical history will include significant medical conditions, diagnosis and/or surgical history occurring prior to informed consent or changes occurring between signing of informed consent and study treatment administration. Medical history events will be classified based on the MedDRA dictionary, version 15.1 (or higher), and summaries will be based on preferred term and system organ class (SOC).

A listing of all medical history will be provided.

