7.4.1 Adverse Events

A treatment-emergent adverse event (TEAE) is defined as any event not present prior to study treatment administration or any event already present that worsens in either intensity or frequency following exposure to study treatment.

Adverse events will be classified based on the Medical Dictionary for Regulatory Activities (MedDRA) dictionary, version 15.1 (or higher). Analyses will be conducted on preferred term and primary system organ class (SOC). All adverse event data will be listed per patient including severity, relationship to study treatment, and action taken. Event severity is based on the World Health Organization (WHO) standard toxicity criteria (STC).

A Dose-limiting toxicity (DLT) will be defined as any grade 3 or 4 event which is at least possibly related to study product or administration procedure.

The adverse event reporting period for this trial begins upon receiving the dose of study treatment and ends 24 months after the administration of SB623.

The following summaries of AEs will be provided:

- TEAEs by MedDRA SOC and by preferred term
- TEAEs by maximum severity (mild, moderate, severe, life-threatening) by MedDRA SOC and preferred term
- TEAEs by relationship to study treatment by not related (includes unrelated and unlikely related) or related (includes possibly, probably, and definitely related) by MedDRA SOC and preferred term.
- AEs resulting in discontinuation from the study, by MedDRA SOC and preferred term
- SAEs by MedDRA SOC and preferred term
- The following listings of adverse events will be provided (TEAEs will be denoted in each listing):
 - o All AEs
 - All Dose-Limiting Toxicities (DLTs)
 - o Adverse events resulting in discontinuation from the study
 - o Deaths (if any)
 - o Serious adverse events
 - AE mappings to MedDRA dictionary terms

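### AE and SAE reporting opens at the first cell dose, so a procedural event between frame placement and the first deposit can fall outside the safety analysis

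*Protocol*

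**What the plan says.** **Start of the window.** Protocol 16.2: "The adverse event reporting period for this trial begins upon receiving the first dose of Study Drug". SAP 7.4.1: "The adverse event reporting period for this trial begins upon receiving the dose of study treatment". Protocol 16.5 gives SAE reporting the same start. On Day 1, Protocol 10.4 lists the AE assessment among the tasks done once the cells are in; before surgery it asks only about changes in medication. SAP section 5 takes baseline as the last assessment before the first infusion, so in the SAP treatment begins with the cells.

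**What happens to earlier events.** SAP 7.4.1 counts as treatment-emergent "any event not present prior to study treatment administration", together with existing events that worsen. SAP 7.2.6 assigns to medical history "changes occurring between signing of informed consent and study treatment administration", and SAP 7.2.8 does the same for signs and symptoms.

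**What comes before the dose.** Protocol 7.0 sets the order on Day 1: frame under local anaesthesia and mild sedation, and a targeting scan; then "One burr-hole craniostomy (1-1.5 cm) is to be fashioned under local anesthesia"; then dural opening, the 1.8-mm stabilizing cannula and the implantation cannula; and only then the first 20 µL deposit.

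**What the plan wants to measure.** Protocol 18.1.1 lists "Adverse events related to the surgical procedure" as a safety parameter, and SAP 6.2 repeats it. The DLT definition (Protocol 9.1 and 14.0, SAP section 5) covers the administration procedure as well as the product. Protocol 14.0 sends surgical infection, bleeding and seizures to the DSMB. Protocol 16.1 marks procedural complications and seizures for expedited reporting.

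**The concern.** The primary objective is the safety of intracranial administration, and the surgery is part of what is being tested. If the reporting window opens only with the cells, the opening steps of that surgery lie outside it in every patient. A patient could have a seizure at dural opening, recover, receive the cells and enter the safety population, with the seizure recorded as history or not recorded at all. The last scheduled history check is at Enrollment, so no visit procedure in Protocol 10 asks about the period between then and the first deposit.

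Two other rules push the same way. Protocol 16.1 defines an AE in terms of a subject who has been given the product. Table 5 in Protocol 16.4 rates causality against the study drug only, and accepts onset too early as a ground for calling an event unrelated. A site that does enter such an event could therefore rate it unrelated, and it would then fail the DLT test of at least possible relation. A serious event in this interval also falls outside Protocol 16.5, so it might not count towards the two SAEs that trigger DSMB review (Protocol synopsis, SAP 7.6).

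**Working it through.** **Step 1: follow specific events through the rules.** Each row concerns a patient who goes to surgery, or would have.

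| Event | Route in the documents | Result |
|---|---|---|
| Seizure at dural opening, resolved before the first deposit | Before the window in Protocol 16.2 and 16.5; history under SAP 7.2.6 if recorded; no imaging route | Not an AE in the window, not a TEAE; yet Protocol 14.0 and 16.1 call for DSMB review and expedited reporting |
| Bleed at dural opening, seen and reported on the Day 2 or Day 8 MRI | SAP 7.4.2 enters reported post-baseline MRI changes as AEs | Has an AE entry; TEAE status depends on the onset assigned |
| New symptomatic stroke or myocardial infarction during a pre-operative hold | Protocol 8.2 criteria 1 and 4; recheck at Baseline (10.3.1); verification before enrollment (10.3.2) | Normally not treated, unless an exception is granted (SAP 4.1) |
| Other harm during such a hold, patient still eligible | Before the window | Same gap as the first row |
| Event at the second or third needle track, or in the post-operative hold | After the first deposit | Inside the window |

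The gap is therefore made up of events that begin before the first deposit, do not worsen afterwards and are not reported as an MRI change.

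**Step 2: the plan's own figure.** Protocol 18.5 gives a chance below 5% of missing a DLT with n = 6 and a true rate of 40%. The chance of seeing none is (1 − 0.40)^6 = 0.6^6 = 0.0467, or 4.67%, so the figure reproduces. It assumes that every DLT is captured.

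**Step 3: how much loss that figure tolerates.** Let f be the share of DLTs that fall in the gap. The documents give no value for f, so it is an assumption. The chance of seeing none becomes (1 − 0.40(1 − f))^6.

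| f | Captured rate | Chance of seeing none |
|---|---|---|
| 0 | 40.0% | 4.67% |
| 1% | 39.6% | 4.86% |
| 5% | 38.0% | 5.68% |
| 10% | 36.0% | 6.87% |

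The 5% limit needs a captured rate of at least 1 − 0.05^(1/6) = 39.3%, so f may be at most 1 − 0.393/0.40 = 1.7%.

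**Step 4: a ceiling from the protocol's own complication rate.** Protocol 2.2.4 cites surgical complications below 1%. Suppose that rate applies here and that every complication precedes the first deposit and is lost.

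- Expected lost events: fewer than 18 × 0.01 = 0.18.
- Chance of at least one in the trial: below 1 − 0.99^18 = 16.5%. In a cohort of 6: below 1 − 0.99^6 = 5.9%.
- If each complication were also a DLT within the 40%, the captured rate would be no lower than 39%, and the chance of seeing none no higher than 0.61^6 = 5.15%.

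**Step 5: the weight of one event.** 1/6 = 16.7% of a cohort; 1/18 = 5.6% of the trial.

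**The case against.** The strongest reply is that other provisions already cover most procedural harm, and much of it stands.

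- **Bleeding.** A reader might infer that an intra-operative bleed vanishes. SAP 7.4.2 gives an MRI-visible bleed an AE entry whatever its onset, and a CT follows implantation directly.
- **Most invasive steps.** A reader might infer that these are all excluded. Of the three needle tracks, the second and third and all later deposits follow the first deposit.
- **DSMB.** A reader might infer that such events never reach it. Protocol 14.0 sends surgical events there with no onset limit, and 16.1 adds expedited reporting. The documents conflict on this; they do not remove the duty.
- **Antithrombotics.** A reader might infer that strokes or infarctions during a pre-operative hold are lost in treated patients. Such an event would normally make the patient ineligible. The hold itself is only implied: Protocol 8.1 says "provided that no antiplatelet, anti-coagulant, or non-steroidal anti-inflammatory drugs are to be restarted after surgery until after the Day 8 MRI is read" and otherwise leaves use to local staff under a guideline. No pre-operative start, duration or share of patients is given, so this exposure cannot be sized. The post-operative part of any hold is inside the window.
- **Start of treatment.** Protocol 18.4 speaks of treatment being initiated without defining it, and the burr hole is described under Cell Administration (10.4) and Treatment Exposure (SAP 7.2.4). The Day 1 AE mark in Table 4 does not by itself bar an intra-operative onset. Some sites may well record these events.
- **Listings.** The SAP lists all AEs and tabulates SAEs without restricting them to TEAEs, so an event that is recorded stays visible.
- **Stopping rule.** The rule of 2 in 6 counts DLTs attributable to the cells, which an event before any cells are given could hardly be.

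None of these provisions captures a non-imaging event before the first deposit. If capture depends on how each of up to 8 sites reads the start of treatment, the counts are not comparable between sites.

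**Conclusion.** The gap is real but narrow. As written, an event such as a seizure between frame placement and the first deposit, which does not later worsen, is outside AE and SAE reporting and is not treatment-emergent. That conflicts with the plan's own procedure-related AE and DLT endpoints and with its DSMB and expedited-reporting rules. Harm from a pre-operative antithrombotic interruption in a patient who stays eligible falls in the same gap, with its extent unknown.

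The likely number of events is small: under 0.18 expected in 18 patients, if the cited rate carries over to this operation and every complication comes early. The sample-size statement has little slack (it fails once f exceeds 1.7%), but under that ceiling it moves only from 4.67% to at most 5.15%. The documents do not support saying that procedural harm in general is hidden. The point matters because one event is 17% of a cohort and the gap lies within the primary objective. It should be fixed; it does not undermine the design.

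**What to change.** 1. In Protocol 16.2, 16.5, 10.4 and Table 4, and in SAP 7.4.1 and its schedule (10.1), start AE and SAE collection at consent or at the first study-mandated intervention, at the latest frame placement.
2. Tabulate procedure-related events before the first deposit with the procedure AEs and DLTs, flagged as before or after the first deposit. The table list in SAP 9.2 shows relationship to study treatment only, so a table or column for relationship to the procedure is needed.
3. Limit SAP 7.2.6 and 7.2.8 to events before the new start point.
4. If dosing is already complete, check the operative and medical records for this interval; Protocol 19.6 makes medical records source data open to the sponsor.

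The cost is wording, a table or column, a few more AE entries and possibly slightly higher reported AE rates. No new visit or test is needed. The same sentences also disagree on when the window closes (24 weeks in Protocol 16.2, 24 months in SAP 7.4.1). That is a separate matter, but it can be reconciled in the same edit.
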